10.11 Participant study completion (week 8)

Patients might terminate their participation in the study at any point. Reason, if available, should be recorded in the patient file. Once participants have completed their week 8 visit (at the hospital/outpatient clinic or as home visit), they will be considered having completed their participation in the study. For those not attending week 8 visit, they will be considered lost to follow up after the three phone call attempts and home visit have occurred. Deaths occurring during the study at patient's household will be documented and relatives will be asked about signs and symptoms before death. In settings where verbal autopsies are routinely conducted (CISM), this data will be considered a study source document and information captured in the off-study-form.

10.12 Retention

Based on previous studies conducted at the sites, we expect a 5% lost to follow up rate at month 2. Sites will implement several strategies to maximize the retention rate, such as recording of several phone numbers in the locator form at recruitment, careful recording of physical address, additional contact information from relatives and friends, travel reimbursement to compensate them for the cost of transport to the clinic for study visits, etcetera, always according to local practice.

10.13 Participant termination and criteria

The study physician responsible and the PI may withdraw a patient from the trial (or certain procedures of the trial) for appropriate medical reasons, because of individual adverse events or new information gained about a diagnostic or a treatment. The physician should contact the Trial Management Team to inform of this decision. Likewise, any patient can withdraw from the study any time without explaining the reasons.

10.14 Trial discontinuation

The study may be discontinued at any time by the funder, sponsor, investigators, or by any of the relevant regulatory bodies and reasons for this decision will be appropriately communicated to the sites and enrolled patients.

10.15 End of trial

The sponsor will notify the authorities of the end of the clinical trial field activities within 90 days of its completion (the date of the last visit of the last patient undergoing the trial).

10.16 Safety Assessments

Refer to Section 10.17

This project is part of the EDCTP2 programme supported by the European Union

Laboratory safety assessments will be done during study site assessment and/or study initiation visits to ensure that potentially infectious specimens are processed according to national and/or international guidelines.

Medical device incidents will be recorded and reported according to the MEDDEV 2.12/1 Rev 8 (see summary in 10.17.1 Medical Device Incidents (including Malfunctions)).

10.17 Safety and Incident Reporting

The probability of an AE or SAE occurring to a trial participant to be associated with the investigational products, or with the additional procedures used (such as sputum and urine collection, venipuncture for those HIV patients and fingerstick), is extremely low.

10.17.1 Serious adverse events (SAE) reporting

An SAE is any unfavourable and unintended sign (including abnormal laboratory finding), symptom or disease temporally associated with the use of an investigational product, whether or not related to the investigational product with a) results in death b) is life-threatening; c) requires inpatient hospitalization or prolongation of existing hospitalization; d) results in persistent disability/incapacity; e) is a congenital anomaly/birth defect or f) requires intervention to prevent permanent impairment or damage to the human subject.

Given the nature of this study (in which no investigational product is administered to the participant), SAE reporting is limited in scope to:

- a) SAEs that may be associated with sputum, urine and blood collection
- b) SAEs which results in death.

SAE reports must be sent to the FIND on a six monthly basis (line listing format). Contacts for SAE reporting can be found on the front of the protocol. SAE reports should be sent to national IRB and regulatory authorities with a similar frequency or as per national regulations for diagnostic clinical trials.

10.17.2 Medical Device Incidents (including Malfunctions)

Medical devices are being provided for use in this Trial for TB diagnosis in PLHIV. In order to fulfil regulatory reporting obligations worldwide, the investigator is responsible for the detection and documentation of events meeting the definitions of incident or malfunction that occur during the

This project is part of the EDCTP2 programme supported by the European Union

trial with such devices. The definition of a Medical Device Incident can be found in Appendix 1.

NOTE: Incidents fulfilling the definition of an SAE related to a medical device will also follow the processes outlined above and in Appendix 1 of the protocol.

10.17.3 Time Period for Detecting Medical Device Incidents

Medical device incidents or malfunctions of the device that result in an incident will be detected, documented, and reported during all periods of the trial in which the medical device is used.

If the investigator learns of any incident at any time after a participant has been discharged from the trial, and such incident is considered reasonably related to a medical device provided for the trial, the investigator will promptly notify FIND.

The method of documenting Medical Device Incidents is provided in Appendix 1.

10.17.4 Follow-up of Medical Device Incidents

The investigator is responsible for ensuring that follow-up includes any supplemental investigations as indicated to elucidate the nature and/or causality of the incident. New or updated information will be recorded on the originally completed form with all changes signed and dated by the investigator.

10.17.5 Reporting of Medical Device Incidents to FIND

Medical device incidents will be reported to FIND within 24 hours after the investigator determines that the event meets the protocol definition of a medical device incident.

The Medical Device Incident Report Form will be sent to the sponsor scanned by e-mail. If e-mail is unavailable, then the investigator should phone the sponsor and send an e-mail as soon as possible. Contact details will be provided in the Trial Manual.

The same individual will be the contact for the receipt of medical device reports. Medical device incidents will then be communicated by the sponsor to the manufacturer within 24 hours after the sponsor has received the Medical Device Incident Report Form.

10.17.6 Regulatory Reporting Requirements for Medical Device Incidents

The investigator will promptly report all incidents occurring with any medical device provided for use in the Trial for FIND to fulfil the legal responsibility to notify appropriate regulatory authorities and other entities about certain safety information relating to medical devices being

This project is part of the EDCTP2 programme supported by the European Union

used in clinical studies.

The investigator, or responsible person according to local requirements (e.g., the head of the medical institution), will comply with the applicable local regulatory requirements relating to the reporting of incidents to the IRB/IEC.

10.18 Retrospective data collection

Given that our control arm may not represent the local standard of care across sites, we will compare the main study endpoints of both study arms with a third cohort of patients, which follows the real standard of care at the different sites. We will retrospectively collect data of a cohort of consecutively hospitalized HIV-positive patients that were admitted prior to the trial initiation. Data to allow the evaluation of primary objectives will be collected from medical records (source documents) in an anonymized fashion. We aim to collect data from patients who were admitted to the site two months or more before the day of the trial first study patient recruitment. Patient records will be selected from consecutive admissions from that day backwards until completing the sample size (around 147 cases per site). Data collection will be obtained retrospectively in order to capture the real practice at the different sites, including potential phone calls to confirm the life status of the patients after two months of hospitalization, minimizing the effect of a potential Hawthorne effect. Given the complexity and often impossibility of obtaining informed consent from patients that have been discharged, no informed consent will be sought for these patients. This IC exemption is an exception contemplated in the International Ethical Guidelines for Health-related Research Involving Humans of the Council for International Organizations of Medical Sciences (CIOMS) (Geneva, 2016). The study has not been powered to detect differences in the primary endpoint between intervention or control arm and the retrospective cohort (which may vary between sites). This is a secondary objective that will be analyzed at site level.

11. Schedule of visits (table 2)

| | Day 0 (recruitment) Control arm | Day 0 (recruitment) Intervention arm | Day 0-3 (<72h) | Daily | At discharge If discharged before day 28/56 | Week 4 | Week 8 +/- 3 days |
|--|--|---|-------------------|-------|---|--------|-----------------------------|
| Baseline Evaluation | | | | | | | |
| Informed consent | X | X | | | | | |
| Eligibility criteria verified | X | X | | | | | |
| CD4 count / Viral Load ^{&} | X | X | | | | | |
| Locator information | X | X | | | | | |
| Brief medical history | X | X | | | | | |
| Proof of HIV status stored | X | X | | | | | |
| WHO Symptom screening | X | X | | | X | | |
| TB Investigations | | Sputum Ultra | | | | | |
| | Urine | Stool | | | | | |
| | AlereLAM# | Ultra | | | | | |
| | Sputum Ultra* | Urine Ultra | | | | | |
| Samples collected and tests | Blood CD4 | Urine AlereLAM | | | | | |
| | | 2x Oral Swabs | | | | | |
| | | Urine FujiLAM | | | | | |
| | | Blood CD4 | | | | | |
| | | Blood for CRP | | | | | |
| Results issued | | | | X | | | |
| Further contacts | | | | | | | |
| Verification TB diagnosis / ad hoc TB investigations | | | | X | X | X | X |
| Verification TB treatment initiation | | | | X | X | X | X |
| Verification vital status | | | | X | X | X | X |
| HIV care / ART | | | | X | X | X | X |

*Sputum Ultra whenever the patient has cough, fever, weight loss or night sweats and/or Ultra on any tissue (including lymph nodes) from patients with suspected extrapulmonary TB

#Urine LAM if patients have currently signs and symptoms of TB (pulmonary and/or extrapulmonary), or with advanced HIV disease (1) or who are seriously ill (2) or else irrespective of signs and symptoms of TB and with a CD4 cell count of less than 200 cells/mm³.

[&]CD4 count testing will be done if not available within the last 3 months. Most recent viral load will be captured (if available)

**urine should be collected in all participants in the control arm, irrespective of whether LAM test is done.

This project is part of the EDCTP2 programme supported by the European Union

12. Laboratory procedures and storage of samples

Samples will be processed and results issued back to attending physicians as soon as possible. AlereLAM results should be available within two hours from specimen collection. Ultra results should be provided within 24 hours from being collected at the participating hospital laboratory associated facilities.

12.1 Xpert Ultra for TB

This WHO recommended assay, which is currently substituting the previous version (Xpert), uses a cartridge-based polymerase chain reaction platform.

12.1.1 Sputum: Ultra testing will be performed in a sample of raw sputum (without any prior decontamination) and it requires mixing sputum with a buffer (proportion 2:1) for 15 minutes. Following incubation, 2ml of the sputum-buffer mix are transferred into the Ultra cartridge, which is placed in the Xpert instrument. Results are ready within 100 minutes. It detects *Mtb* DNA in a sputum sample and is able to detect a mutation in the resistance-determining region (RRDR) of the *rpoB* gene which is the responsible of 95% of drug resistance to rifampicin (Rif).³³ Rifampicin resistance is generally considered to be predictive of MDR since most Rif resistant strains are also resistant to isoniazid.

12.1.2 Stool: Ultra testing on stool will be done in a sterile loop from bulk stool following the KNCV SOS method (<https://www.kncvtbc.org/en/sos-stoolbox/>).

12.1.3 Urine: Following the removal of 200 µL of urine for AlereLAM testing (see below) and 12 ml for storage for future testing the remaining urine (around 40-50mls) will be cooled centrifuged at 3000g for 15mins in a bucket centrifuge. The supernatant will be discarded, and the urine pellet resuspended in approximately 2ml of PBS. 0.75ml of the resuspended pellet will be added to 1.25ml of Ultra sample reagent and incubated for 15 minutes, then added to the cartridge and processed as per the manufacturer's instructions.

12.1.4 Tongue swab: After the sample is collected (from brushing the swab along the length/breadth of the anterior 2/3 of the tongue dorsum for about 10 seconds) the head of the swab will be broken off and the shaft of the swab discarded. The tubes will be stored dry and later Ultra and/or LumiraDx (see 12.3) testing will be performed following instructions in SOPs developed.

This project is part of the EDCTP2 programme supported by the European Union

12.2 Other urine-based tests procedures:

12.2.1 AlereLAM testing:

Recommended by WHO for TB diagnosis in severely immunocompromised HIV-positive patients, will be performed under the specified criteria in the control arm and in all participants in the intervention arm. A urine sample (at least 1-3 ml) will be taken at the hospital facilities (see below). The test is performed by applying 60 µL of unconcentrated urine to the Alere Determine™ TB LAM Ag assay strip and incubating at room temperature for 25 minutes (time-set). The strip is then inspected by eye.

The intensity of any visible band on the test strip is graded by comparing it with the intensities of the bands on a manufacturer-supplied card (LAM positive will be deemed using the grade 1 cut-off on the manufacturer's post 2014 reference card). AlereLAM tests will be interpreted by two independent readers at the clinic, and results will be recorded. In case of discrepancy, a third reader will be used as a tie-breaker. Invalid tests will be repeated using the same urine. Indeterminate results will be repeated with a different urine sample. Alere-LAM test strips will be stored until the end of the study for data monitoring purposes. Alere-LAM tests will be read prior to the results of the sputum Ultra (if performed) and without knowing any clinical details of the patient to reduce bias.

12.2.2 FujiLAM testing (Appendix 2): Briefly, urine is added to the reagent tube up to the indicator line (approximately 200 µL), mixed, and incubated for 40 min (set timer) at ambient temperature. Aftermixing again, two drops of urine are added to the test strip. Following this, button two is immediately pressed to release a reducing agent for silver amplification. After the Go Next colour indicator mark turns orange (within 3–10 min), button 3 is pressed to release a silver-ion solutionto activate the silver amplification reaction. The result has to be read within 10 min (set timer). TheFujiLAM assay does not use a reference scale card and any line identified on the test line is deemedpositive. This test will be done retrospectively in banked samples.

12.3 LumiraDx: The test strip is introduced into the LumiraDx device through opening the instrument's door. A drop of the prepared oral tongue swab / blood specimen is applied to the test strip and a confirmation of the sample detection appears in the instrument's screen. After this, the door is closed immediately. The results are provided with in 10 minutes.

12.4 HIV testing: Rapid point-of-care antibody-based HIV testing will be performed in those patientswith unknown or undocumented HIV status using fingerprick blood. Testing will be done by trained health care workers. If the result of the first "rapid" test (Determine®, Abbott Laboratories, USA) is positive, a second confirmatory test will be performed. CD4 counts will be obtained fromTB cases coinfected with HIV (if no recent documented CD4 counts are available-within last 3 months)

This project is part of the EDCTP2 programme supported by the European Union

as well as all newly identified HIV-positive cases. CD4 testing will be done at each site using point of care PIMA equipment or FACSCalibur flow cytometers. Newly diagnosed HIV- positive patients will be referred to appropriate counselling services at each of the sites.

12.5 Sample Storage details:

Storage of all specimens will follow detailed SOP which will be similar at all participating sites.

Specimen storage is not a mandatory component of the protocol, but will be encouraged to accomplish exploratory objectives and retrospective testing. Storage should be done the same day of sample collection.

12.5.1 Urine samples. After removing necessary volumes for Ultra and AlereLAM testing, transfer raw urine (12 ml) to a sterile 50ml tube. Aliquot the supernatant in two 3.5 ml aliquots. Aliquots should be stored at -80 or -70°C. In case no criteria for AlereLAM testing is in place in the control arm, urine would still be collected for storage.

12.5.3 Tongue swabs samples: Two tongue swabs will be collected. After sample collection, the head of both swabs will be broken off and stored dry in a 5ml tube at -80°C for later testing with Ultra and the LumiraDx platform.

This project is part of the EDCTP2 programme supported by the European Union

13. Statistical considerations and data analysis

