8.1 Primary Endpoint(s)

The primary endpoint is:

- The proportion of participants diagnosed with microbiologically confirmed TB and started on TB treatment within 72 hours of enrolment, separately for intervention and control arm. The numerator is the number of participants per study arm who are diagnosed with microbiologically confirmed TB and start on treatment within 72 hours of enrolment. The denominator is the number of participants enrolled per study arm. We will compare this indicator between both study arms. Patients are defined to have microbiologically confirmed TB if at least one confirmatory TB test (Ultra, AlereLAM) gives a positive result.

Hospitalized PLHIV experience high mortality and TB underdiagnosis and misdiagnoses are frequent. TB diagnosis is important when you can quickly start appropriate therapy. This endpoint will capture both diagnostic dimensions of the intervention (higher rates of *Mtb* laboratory confirmation) as well as the relevant patient outcome (TB treatment initiated).

Diagnostic procedures and treatment initiation (if appropriate) should be completed within 72 hours of enrolment given the intervention is aimed at rapid collection of samples for all patients upon admission and that Ultra testing can provide results within a few hours from specimen collection at all participating sites.

The numerator of the primary endpoint also includes patients whose bacteriological confirmation might arrive after 72 hours of enrolment. There might be cases where liquid or solid culture might be requested and results arrive after 72 hours. If the patient had been put on treatment empirically (before a positive culture results has arrived), that case will contribute to the numerator, given that treatment would have been started in a "true" TB case.

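### Protocol 12.1.3 and 12.5.1 divide the urine specimen in opposite orders; on a short void, 12.1.3 puts optional storage ahead of urine Ultra, a primary-endpoint test in the intervention arm only

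*Protocol*

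**What the plan says.** Protocol 12.1.3 describes urine Ultra. It begins "Following the removal of 200" microlitres for AlereLAM and goes on: "12 ml for storage for future testing the remaining urine (around 40-50mls) will be cooled centrifuged". Ultra receives the remainder.

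Protocol 12.5.1 describes storage of the same specimen: "After removing necessary volumes for Ultra and AlereLAM testing, transfer raw urine (12 ml) to a sterile 50ml tube". Here storage receives the remainder. The next instruction is "Aliquot the supernatant in two 3.5 ml aliquots", with no spin step given between the raw urine and the supernatant.

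On the standing of storage, Protocol 12.5 says: "Specimen storage is not a mandatory component of the protocol, but will be encouraged to accomplish exploratory objectives and retrospective testing".

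On the standing of urine Ultra, Protocol 8.1 counts a participant as confirmed "if at least one confirmatory TB test (Ultra, AlereLAM) gives a positive result". SAP 4.4 lists the urine Ultra result among the variables that determine confirmation. Protocol 10.9.1 and 10.9.2 plan urine Ultra for the intervention arm and not for the control arm.

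The only minimum urine volume stated is for AlereLAM, in Protocol 12.2.1: "A urine sample (at least 1-3 ml) will be taken at the hospital facilities". Neither document gives a minimum for urine Ultra or a rule for dividing a short specimen.

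**The concern.** When there is too little urine for everything, the order of the draws decides which use goes short. Under 12.1.3 it is the Ultra pellet; under 12.5.1 it is the biobank. The first outcome inverts the trial's own priorities, because a non-mandatory store for exploratory work is filled before a test that can make a participant a primary-endpoint success.

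The effect would be one-sided. Only the intervention arm has planned urine Ultra, so any lost yield could only reduce that arm's confirmed proportion and move the comparison toward no difference. Protocol 13.1 relies on this specimen: it attributes 4 percentage points of added yield to urine Xpert and about 1 to stool, within a 7-point target difference. A missing urine Ultra could also remove a participant from the per-protocol set in SAP 6.1.1, which requires all required samples and results within 72 hours.

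A smaller issue concerns the banked material. Since 12.5.1 names both raw urine and supernatant without a spin step, it is unclear what the later FujiLAM evaluation would be run on.

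**Working it through.** **1. Specimen implied by 12.1.3.** Inputs from that section: 0.2 ml for AlereLAM, 12 ml for storage, 40 to 50 ml left for Ultra.

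- Lower end: 0.2 + 12 + 40 = 52.2 ml
- Upper end: 0.2 + 12 + 50 = 62.2 ml

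At these volumes 12.5.1 gives the same result: 0.2 ml and 40 to 50 ml are removed, and 12 ml remains to store. The conflict matters only below about 52 ml.

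**2. Shorter voids.** The documents give no void volumes, so V is assumed.

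- Storage first (12.1.3): Ultra gets V − 0.2 − 12, and not less than zero.
- Ultra before storage (12.5.1): Ultra gets at most V − 0.2. This is a maximum, because 12.5.1 does not define the volume Ultra needs.
- Share of post-AlereLAM urine taken by storage under 12.1.3: 12 / (V − 0.2).

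| Assumed void V (ml) | Ultra, storage first (ml) | Ultra, before storage, at most (ml) | Share taken by storage |
|---|---|---|---|
| 40 | 27.8 | 39.8 | 30% |
| 30 | 17.8 | 29.8 | 40% |
| 20 | 7.8 | 19.8 | 61% |
| 15 | 2.8 | 14.8 | 81% |
| 12.2 | 0 | 12.0 | 100% |

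**3. The plan's sample size, as a base.** With 19% vs 26%, two-sided alpha 0.05 and 80% power, the normal-approximation formula gives 558 per arm. 558 × 1.05 = 585.9, which reproduces the stated 586. After 5% loss, 586 × 0.95 ≈ 557 per arm, with power 80.0%. The sample size is not in dispute.

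**4. Illustration of the effect on power.** Suppose the whole added yield y of urine Ultra is lost in a share f of intervention participants. The intervention proportion becomes p2 = 0.26 − y × f. With p1 = 0.19, n = 557 and p̄ = (p1 + p2)/2:

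power = Φ{ [ |p2 − p1| √n − 1.96 √(2 p̄(1 − p̄)) ] / √( p1(1 − p1) + p2(1 − p2) ) }

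Three values of y can be drawn from the protocol:

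- 1.56 points: section 5.2 cites a trial in which urine Xpert was the only positive test in 6% of confirmed patients; 0.06 × 26% = 1.56.
- 4 points: section 13.1, for urine Xpert.
- 4.7 points: 4 × 1.17, the upper end of the relative gain for Ultra over Xpert in section 13.1.

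| Assumed f | y = 1.56 | y = 4 | y = 4.7 |
|---|---|---|---|
| 0% | 80.0% | 80.0% | 80.0% |
| 5% | 79.1% | 77.8% | 77.4% |
| 10% | 78.3% | 75.4% | 74.6% |
| 20% | 76.5% | 70.4% | 68.5% |

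The shares f are not in the documents. For a given f and y these are worst cases, because a smaller pellet does not always turn a positive result negative. The 19% and 26% are also confirmation proportions, whereas the endpoint additionally requires treatment started within 72 hours.

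**The case against.** The strongest reply is that the two sections agree for the specimen the protocol has in mind and that safeguards cover the rest. Storage is optional, so a site with little urine may skip it without breaching the protocol. AlereLAM is drawn first in 12.1.3, and sputum and stool Ultra do not depend on urine. Protocol 10.9.1 allows collection up to 72 hours and encourages drinking; 10.9.2 has late samples still collected and processed. Protocol 10.7 promises common laboratory SOPs and training, and 12.5 defers storage to a detailed SOP. The SOPs are not among the documents and may already settle the order.

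Most of this stands, and it limits the size of the problem. It does not remove it. The extended window helps a patient who has passed no urine but does not say how to divide a short specimen. Optional storage permits a site to protect Ultra, but 12.1.3 read literally tells it to do the opposite. An SOP that fixes the order would have to depart from one of the two sections.

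Two stronger readings are tempting and not supported. A reader might infer that intervention-arm confirmation will be lowered, or will vary by site. The documents give neither void volumes nor a relation between volume and yield: the pellet is resuspended in about 2 ml and 0.75 ml of it is tested, so share of volume is not share of yield. Divergence between sites is conjecture given the shared SOPs.

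A reader might also infer that the 12 ml draw is excessive, since two aliquots of 3.5 ml make only 7 ml and FujiLAM uses about 200 microlitres. But 12.5.1 aliquots supernatant, so the other 5 ml may be pellet or dead volume, and storage is for future testing generally. A cut to 7 ml is not justified.

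**Conclusion.** The contradiction between 12.1.3 and 12.5.1 is explicit and worth correcting. It has no effect at the nominal 52 to 62 ml. On shorter voids, 12.1.3 gives non-mandatory storage priority over a test that counts toward the primary endpoint in one arm only, and at 12.2 ml or less it leaves nothing for that test. The direction of any effect is toward no difference.

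Its frequency and size cannot be determined from the documents. The power figures show only what assumed losses would do and are not an estimate for this trial. Nor could the question be examined from the variables listed in SAP 4.4, which include no urine volume. The point does not change the stated sample size. It is a procedural inconsistency with a plausible but unquantified route to the primary endpoint, and it is cheap to remove.

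**What to change.** Reconcile Protocol 12.1.3 with 12.5.1, and the laboratory SOP with both:

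- Draw the AlereLAM volume first, then Ultra up to its target volume, then storage from what is left. State that storage is reduced or skipped when volume is short.
- Record the volume centrifuged for urine Ultra, so that its relation to yield can be examined.
- State whether the banked aliquots are raw urine or supernatant and, if supernatant, give the spin step. Leave the 12 ml draw as it is for full specimens.

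The cost is a wording change in the protocol and SOP and one data field. The downside is that some low-volume participants will have less or no banked urine for exploratory FujiLAM testing, so that evaluation may under-represent them.
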